# 9.3.2 Variables

Only the data collected as part of routine medical care will be captured using the eCRF by the investigator (patient-reported questionnaires will be completed directly by the participant on paper and returned to the site for data entry into the eCRF). If some assessments are not routinely performed by the investigator, they will not complete the corresponding sections in the eCRF.

**PAGE 52 OF 287** 

The FOPal registry captures individual participants' data as follows:

### 9.3.2.1 Demographic and Baseline Characteristics

The FOPal registry study will collect the following data at the Baseline Visit if available:

- Baseline demographics including date of birth, gender and race, where permitted;
- Reason for absence of treatment for unexposed participants, when available;
- Physical examination (only if clinic visit) including a general assessment as well as dermatologic, lymph nodes, HEENT, chest, cardiac, abdomen, limb/extremities, musculoskeletal, neurologic and other assessments (as per routine clinical care) for all participants at the Baseline Visit, at the first marketed palovarotene intake for exposed non-naïve participants and at the Follow-up/End of Study Visits;
- Medical or surgical history, excluding FOP-related history, within the 12 months before the signed informed consent date for exposed naïve or unexposed participants and within the past 12 months prior to the first marketed palovarotene intake for exposed non-naïve participants;
- FOP history including the date of symptom onset, date of diagnosis by a physician, method of diagnosis, date of genetic test if performed and type of FOP genetic variant;
- Number of flare-ups over the past 12 months prior to the first marketed palovarotene intake and until the signed informed consent date for exposed non-naïve participants or 12 months preceding the signed informed consent date for exposed naïve or unexposed participants;
- Movement mobility history within the 12 months before the signed informed consent date for exposed naïve or unexposed participants and over the past 12 months prior to the first marketed palovarotene intake and until the signed informed consent date for exposed non-naïve patients. The latter includes locations, mobility impact start date, change in movement, change in extra bone growth, symptoms if preceded by a flare-up event and causes.

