**PAGE 43 OF 287** 

 Table 4
 Schedule of Assessments: Unexposed Participants

Assessment/Procedure	Retrospective Period * (12 Months before baseline)	Baseline Visit	Follow-Up Visits (as per routine clinical practice[a])/ End of Study Visit [j]
Clinic visit or telephone/video contact visit		X	X
Informed consent [b]		X	
Inclusion/exclusion criteria		X	
Baseline demographics		X	
Physical examination [c,d]	X [i]	X	X
FOP history	X		
Growth status assessment (bone age, knee height and epiphyseal status) [d,e]	X [i]	X	X
Tanner staging	X [i]	X	X
Linear height and weight [d]	X	X	X
Vital signs [d,f]	X [i]	X	X
medications	X	X	X
Concomitant surgery and non-drug therapies	X	X	X
Spirometry and DLCO test [d,g]	X [i]	X	X
CAJIS [d]	X [i]	X	X
Movement mobility history (including flare-ups)	X		
Movement mobility changes (including flare-ups)		X	X
Medical events of special interest	X	X	X
Participant Questionnaires:			1
FOP-PFQ assessment [h]		X	X
PROMIS Global Health Scale [h]		X	X
FOP assistive devices assessment [h]		X	X

CAJIS=Cumulative Analogue Joint Involvement Scale; DLCO=Diffusion Capacity of the Lung for Carbon Monoxide; FEVi=Forced Expiratory Volume in one second; FOP=Fibrodysplasia Ossificans Progressiva; FOP-PFQ=FOP-Physical Function Questionnaire; FVC=Forced Vital Capacity; HEENT= head, eyes, ears, nose and throat; PROMIS=Patient-Reported Outcomes Measurement Information System;.

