# For exposed naïve participants (Table 2)

- Baseline demographics;
- Physical examination including a general assessment as well as dermatologic, lymph nodes, head, eyes, ears, nose and throat (HEENT), chest, cardiac, abdomen, limb/extremities, musculoskeletal, neurologic and other assessments (as per routine clinical care);
- Medical or surgical history (12 months before the Baseline Visit);
- FOP history (date of symptom onset, date of diagnosis by a physician, method of diagnosis, date of genetic test if performed and type of FOP genetic variant);
- Growth status assessment for growing children (bone age, knee height and epiphyseal status assessment);
- Tanner staging for growing children;
- Linear height and weight (linear height within 6 to 12 months prior to the Baseline Visit will also be collected);
- Vital signs (respiratory rate, blood pressure and heart rate);
- Pregnancy test (as per local label, participants are assessed for child-bearing status and pregnancy prevention measures. These conditions also concern participants who are not currently sexually active unless the prescriber considers that there are compelling reasons to indicate that there is no risk of pregnancy);
- Prior (two months before the Baseline Visit) and concomitant medications;
- Concomitant surgery and non-drug therapies;
- Prior use of palovarotene (investigational product);
- Marketed palovarotene dose for chronic and flare-up treatment;
- Spirometry and DLCO test;
- CAJIS for FOP;

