#### 9.2.7.2 Baseline Visit for Unexposed Participants

Investigators at participating FOPal registry sites will identify participants who fulfil the inclusion and exclusion criteria. Signed informed consent should be obtained prior to enrolment according to local regulations and once inclusion and exclusion criteria have been satisfied. If the participant is <18 years old (or the legal age of consent in the jurisdiction in which the study is taking place), assent and parent or legally authorised representative consent will also be required.

The participants will attend a clinic (preferred) or telephone/video visit and assessments will be performed according to routine clinical care. The following variables will be captured from Baseline Visit records as available (Table 4):

- Baseline demographics;
- Physical examination including a general assessment as well as dermatologic, lymph nodes, HEENT, chest, cardiac, abdomen, limb/extremities, musculoskeletal, neurologic and other assessments (as per routine clinical care);
- FOP history (date of symptom onset, date of diagnosis by a physician, method of diagnosis, date of genetic test if performed and type of FOP genetic variant);
- Growth status assessment for growing children (bone age, knee height and epiphyseal status assessment);
- Tanner staging for growing children;
- Linear height and weight;
- Vital signs (respiratory rate, blood pressure and heart rate);

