## 9.6.1 Data Collection

The specific data to be collected at each visit, if available, are summarised in the Schedule of Assessments (Table 2, Table 3 and Table 4).

All relevant data collected as part of routine medical care will be captured using the eCRF by the investigator (patient-reported questionnaires will be completed directly by the participant or proxy on paper and returned to the site for data entry into the eCRF) and transmitted to the sponsor. If some assessments are not routinely performed by the investigator, they will not complete the corresponding sections in the eCRF.

Data will be collected in an eCRF via the internet utilising a secured website. The sponsor and the SP will ensure that the eCRF developed is appropriate to capture the data required by the protocol. The sponsor will ensure that the entrusted SP uses adequate technology to ensure data security transfer and backup.

Each site is required to have a computer and internet connection available for site entry of clinical data. Data entry in the eCRF will be performed by the investigator or by the designated person from their team and to ensure confidentiality and security of the data, all entries into the eCRF will be made under the electronic signature (e-signature) of the person performing the action (username and password). Only sponsor-authorised users will be given access to the eCRF as appropriate for their study responsibilities. All users must have successfully undergone software application training prior to entering data into the eCRF.

Once written informed consent (and assent, if applicable) has been obtained, the eCRF will provide a numeric participant identifier to pseudonymise the data from each participant. Data for each participant must be entered into the eCRF within 5 days of the participant's enrolment, each Follow-Up Visit and the End of Study Visit. Data transmitted will be pseudonymised and will be identified only by the participant number. Only investigating sites will be able to link the numeric identifier to each participant's identity.

In compliance with Good Pharmacoepidemiology Practices (GPP), the participant's medical records should be clearly marked and permit easy identification of their participation in this study.

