# Matching of Exposed Participants to Unexposed Participants

The Safety Exposed Population will be matched with the Safety Unexposed Population. To minimise potential selection bias resulting from differences between these two populations, the PS method will be employed with the Inverse Probability of Treatment Weighting (IPTW) method, ensuring that both populations are balanced concerning crucial baseline variables.

For constructing the PS model, logistic regression will be used. This model will encompass essential baseline covariates (at index date), including age, gender, time since the last flare-up, and the total CAJIS score. Additional covariates may be included if deemed necessary. Balance diagnostics before and after applying weights will be reviewed to assess if there is any important residual imbalance. Standardised mean differences (SMDs) will be used to compare baseline covariates and estimated propensity scores between exposed and unexposed populations. SMDs greater than 0.1 for individual covariates on the weighted sample signify residual imbalance that may lead to biased results. A density plot of the estimated propensity scores by population will be generated to visually inspect the amount of overlap between the populations. A box plot of the propensity score weights for the unexposed population will also be generated to visually inspect for highly influential observations.

Other methods will be detailed in the SAP if needed.

The number and proportion of missing data for each baseline covariate to be included in the propensity score model will be reported for exposed and unexposed populations. The analysis

PAGE 66 OF 287

methods will proceed as a complete case analysis if, and only if, the proportion of participants in the unexposed participants with at least one missing value among variables required for the model is less than 5%. Otherwise, in addition to the complete case analysis, multiple imputation will be used as a sensitivity analysis to handle missing data. The methods to evaluate the effect of missingness and to handle missing data will be detailed in the SAP.

For participants who start palovarotene (or any investigational or commercialised FOP treatment) after being in the unexposed population, only their data until palovarotene intake with a minimum of 6 months of data collected will be included in the analysis.

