#### 9.7.3.5 Other Analyses

Demographic and Baseline Characteristics

Demographic and Baseline data will be included in the participant data listings using the Safety Exposed and the Safety Unexposed Populations.

Descriptive statistics of demographic and Baseline data will be presented for the Safety Exposed and the Safety Unexposed Populations.

Medical and surgical history will be coded using MedDRA and summarised.

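### Table 4 and section 9.2.7.2 omit two baseline items that section 9.3.2.1 requires for unexposed participants: medical or surgical history and the reason for not being treated

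*Protocol*

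**What the plan says.** Section 9.3.2.1 of the protocol sets out what the registry will collect at the Baseline Visit if available. Two of its bullets concern the unexposed cohort and matter here: "Reason for absence of treatment for unexposed participants, when available", and "Medical or surgical history, excluding FOP-related history, within the 12 months before the signed informed consent date for exposed naïve or unexposed participants". The second gives unexposed participants a look-back window of their own, so collection was clearly intended.

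The operational text for the same cohort is Table 4 ("Schedule of Assessments: Unexposed Participants") and the list in section 9.2.7.2, introduced by "The following variables will be captured from Baseline Visit records as available (Table 4". Neither contains either item.

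For exposed participants, Tables 2 and 3 both have a row for medical or surgical history. Section 9.2.7.1 repeats it for naïve participants as "Medical or surgical history (12 months before the Baseline Visit", and for non-naïve participants with a window anchored on the first marketed dose.

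On which text governs data capture, section 9.6.1 states: "The specific data to be collected at each visit, if available, are summarised in the Schedule of Assessments", naming Tables 2, 3 and 4. Section 9.1 likewise presents Table 4 as the description of the data collected for unexposed participants. On analysis, section 9.7.3.5 plans baseline statistics for both safety populations and adds: "Medical and surgical history will be coded using MedDRA and summarised".

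**The concern.** Sections 9.1 and 9.2.5 recruit unexposed participants at the same sites as the exposed, in places where palovarotene is marketed. Why these people are untreated is therefore a basic question about the comparator. It is sharpened by the eligibility rules. Section 9.2.1.2 keeps out of the exposed cohort people in whom palovarotene is contraindicated, apart from a pregnancy exception, while section 9.2.2.2 has no matching exclusion. The comparator may then include people who could not have been treated, which is a positivity problem for inverse probability weighting. The reason for absence of treatment is the listed variable that would show this directly.

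Medical history matters in a different way. Section 9.7.3.4 weights the cohorts to limit selection bias, leaves room for further covariates, and treats a standardised mean difference above 0.1 as residual imbalance. A comorbidity variable held for the exposed cohort only can be neither modelled nor checked in this way. The statistical analysis plan can choose covariates, but it cannot restore data that were never captured.

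**Working it through.** No figure in the protocol is at stake, so the check is a comparison of the passages.

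| Item for unexposed participants | 9.3.2.1 | Table 4 | 9.2.7.2 |
|---|---|---|---|
| Medical or surgical history, 12 months before consent | yes | no | no |
| Reason for absence of treatment | yes, when available | no | no |
| Items present | 2 of 2 | 0 of 2 | 0 of 2 |

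**Is the omission an artefact of a broken table?** No. The bullet list in section 9.2.7.2 is intact and lacks the items independently of Table 4. The exposed lists in section 9.2.7.1 run physical examination, medical or surgical history, FOP history. The unexposed list goes straight from physical examination to FOP history.

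**Does it touch the planned propensity-score model?** Section 9.7.3.4 describes the essential covariates as "including age, gender, time since the last flare-up, and the total CAJIS score". None of these four is a disputed item (0 of 4). Table 4 and section 9.2.7.2 both carry demographics, CAJIS and movement mobility history with flare-ups. Time since the last flare-up is not itself a listed field, but that is unrelated to the two missing items.

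**What else in Table 4 bears on comorbidity?** Three rows are marked for the 12-month retrospective period and at Baseline:

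- medications, collected with the reason for prescription (section 9.3.2.2);
- concomitant surgery and non-drug therapies, where surgery carries an indication and a reason (section 9.3.2.3);
- medical events of special interest, which include growth outcomes and fractures (section 9.3.2.6). Section 9.3.2.7 confirms that fractures in the 12 months before consent are recorded on those pages.

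These overlap with a non-FOP medical history without replacing it. No row in Table 4 is labelled as holding the reason for non-treatment.

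**Upper bound on the loss.** If sites followed Table 4 alone, up to 33 of the planned minimum of 33 unexposed participants would lack both items, against medical history scheduled for all of the minimum 67 exposed.

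**Consequence if comorbidity were later added to the model.** Section 9.7.3.4 allows a complete-case analysis alone only when fewer than 5% of unexposed participants lack a required covariate. With 33 unexposed:

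- 1/33 = 3.0%, within the limit;
- 2/33 = 6.1%, beyond it;
- 33/33 = 100%, which leaves no complete unexposed case and no observed unexposed value on which to base the multiple imputation that the section offers as a sensitivity analysis.

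This last step is conditional: no such covariate is planned at present.

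**The case against.** The strongest reply is that section 9.3.2.1 already says both items will be collected. Section 9.6.1 says only that the schedules summarise the data, and it also requires an eCRF suited to what the protocol demands, which includes section 9.3.2.1. The eCRF is not among the documents. The reason for non-treatment is qualified by availability and sits in the same subsection as date of birth, gender and race, which share a single demographics row in Table 4, so it could be recorded there. All of this stands to the extent that non-collection is a risk and not something the protocol fixes. It does not remove the conflict: a site reading Table 4 and section 9.2.7.2 is prompted for neither item. Section 9.3.2.1 also gives the reason for non-treatment its own bullet, separate from demographics.

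A reader might infer more than the documents support:

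- *That the comparator's main confounding data are lost.* The protocol names its essential covariates, and neither item is among them. Adding others is optional.
- *That earlier fractures would be missing for the comparator.* Those in the 12 months before consent are scheduled as medical events of special interest.
- *That the baseline table would show a falsely healthier comparator.* Section 9.7.3.1 requires missing data to be counted and percentages to use non-missing observations, so an uncollected item should appear as missing and not as absence of disease.
- *That the reason for non-treatment belongs in the balance diagnostics.* It is undefined for exposed participants, so no standardised difference between cohorts exists.

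The comparison is also descriptive, with estimates and 95% intervals and no hypothesis tests. That limits the stakes but does not remove them, since an estimate can be confounded whether or not it is tested.

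**Conclusion.** The inconsistency is certain; its effect on the data is a risk. Two baseline variables required for unexposed participants by section 9.3.2.1 are absent from both operational texts for that cohort, while medical history is scheduled throughout for the exposed.

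If sites work from Table 4, comorbidity information becomes one-sided, and the record of why comparators are untreated may be lost. The worst case is the whole unexposed cohort, and it assumes that Table 4 prevails over section 9.3.2.1 at every site and in the eCRF. The 33 and 67 are planned minimums, not fixed totals.

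The point should be corrected, and soon. Data collection was planned to start in Q4 2024, so for anyone already enrolled the remedy is retrospective chart retrieval.

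**What to change.** Add two entries to Table 4 and to the list in section 9.2.7.2, matching section 9.3.2.1:

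- *Medical or surgical history (12 months before consent)*;
- *Reason for absence of treatment (when available)*.

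Confirm that the eCRF for unexposed participants holds both.

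In the analysis, summarise medical history in the exposed and unexposed populations and include it in the balance diagnostics of section 9.7.3.4. Summarise the reason for non-treatment descriptively, in the unexposed population only.

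The cost is brief chart entry for at least 33 participants and one eCRF field specific to the unexposed cohort. A medical-history form is already needed for the exposed. No additional test or visit is involved.

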**PAGE 42 OF 287** 

AE=Adverse Event; AESI=Adverse Event of Special Interest; CAJIS=Cumulative Analogue Joint Involvement Scale; CT= Computed Tomography; DLCO=Diffusion Capacity of the Lung for Carbon Monoxide; FEV1=Forced Expiratory Volume in one second; FOP=Fibrodysplasia Ossificans Progressiva; FOP-PFQ=FOP-Physical Function Questionnaire; FVC=Forced Vital Capacity; HEENT= head, eyes, ears, nose and throat; PI=Prescribing Information; PROMIS=Patient-Reported Outcomes Measurement Information System; SAE=Serious Adverse Event.

- a Follow-up Visits are recommended every 6 months, or as per local label.
- b If participant <18 years (or the legal age of consent in the jurisdiction in which the study is taking place), assent and parent or legally authorised representative consent will also be required.
- c This includes a general assessment, dermatologic, lymph nodes, HEENT, chest, cardiac, abdomen, limb/extremities, musculoskeletal, neurologic and other.
- d Not expected in the context of a telephone/video visit.
- e Collected for growing children. Assessment as per local label.
- f Linear height within 6 to 12 months prior to first marketed palovarotene intake.
- g Vital signs to be collected are respiratory rate, blood pressure and heart rate.
- h Participants will be assessed for child-bearing status and pregnancy prevention measures. As per local label, pregnancy testing is carried out with a confirmation of absence of pregnancy monthly if the participant receives palovarotene and one month after stopping. These conditions also concern participants who are not currently sexually active unless the prescriber considers that there are compelling reasons to indicate that there is no risk of pregnancy.
- This includes a period of two months prior to the first marketed palovarotene intake.
- j Not applicable for pregnant participants.
- k Spirometry obtains the lung function parameters of observed and % predicted FVC and FEV1 and the absolute and % predicted FEV1/FVC ratio. The DLCO test obtains observed and % predicted DLCO which provides information on the efficiency of gas transfer from alveolar air into the bloodstream.
- 1 This includes number of flare-ups over the past 12 months before the first marketed palovarotene intake.
- m Spinal health assessment to be performed using radiological imaging (e.g. CT, X-ray, scintigraphy, etc).
- n AE, SAE, Special Situation and AESI collection begins once the informed consent has been signed.

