#### For exposed non-naïve participants (Table 3):

- Baseline demographics;
- Physical examination including a general assessment as well as dermatologic, lymph nodes, HEENT, chest, cardiac, abdomen, limb/extremities, musculoskeletal, neurologic and other assessments (as per routine clinical care);
- Medical or surgical history (12 months before the first marketed palovarotene intake);
- FOP history (date of symptom onset, date of diagnosis by a physician, method of diagnosis, date of genetic test if performed and type of FOP genetic variant);
- Growth status assessment for growing children (bone age, knee height and epiphyseal status assessment) at the first marketed palovarotene intake and at the Baseline Visit;
- Tanner staging for growing children at the first marketed palovarotene intake and at the Baseline Visit:
- Linear height and weight from the first marketed palovarotene intake and at the Baseline Visit (linear height within 6 to 12 months prior to the first marketed palovarotene intake will also be collected);
- Vital signs (respiratory rate, blood pressure and heart rate);
- Pregnancy test (as per local label, participants are assessed for child-bearing status and pregnancy prevention measures. These conditions also concern participants who are not currently sexually active unless the prescriber considers that there are compelling reasons to indicate that there is no risk of pregnancy);
- Prior (two months prior to the first marketed palovarotene intake and until the Baseline Visit) and concomitant medications;
- Concomitant surgery and non-drug therapies;
- Prior use of palovarotene (investigational product);
- Marketed palovarotene dose for chronic and flare-up treatment;
- Spirometry and DLCO test at the first marketed palovarotene intake and at the Baseline Visit:

PAGE 47 OF 287

- CAJIS for FOP at the first marketed palovarotene intake and at the Baseline Visit;
- Movement mobility history, including flare-ups (over the past 12 months prior to the first marketed palovarotene intake and until Baseline Visit);
- Movement mobility changes, including flare-ups (from Baseline Visit);
- Spinal health assessment using radiological imaging (e.g. CT, X-ray, scintigraphy, etc) at the first marketed palovarotene intake and at the Baseline Visit;
- Retrospective important medical events related to the disease (including vertebral fractures) at the first marketed palovarotene intake and until the Baseline Visit;

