#### Flare-ups

At Baseline, the investigator will ask the participant how many flare-ups they experienced over the past 12 months. At each Follow-up Visit, the investigator will ask the participant how many flare-ups they experienced since the last visit.

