## Mobility change

Any movement mobility change (better/the same/slightly worse/moderately worse/severely worse movement) will be summarised by body locations and annually.

Actual values as well as the change from the Baseline Visit in number of impacted locations per patient will be presented annually.

The evolution of impacted location will be presented annually by summarising for each location (some grouping might be done) the number of times the location is impacted.

Movement mobility outcomes (change in extra bone growth, change in movement), causes, associated symptoms if preceded by a flare-up will be summarised by location.

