# Flare-ups

The number of flare-ups over the past 12 months prior to baseline and since the last visit will be presented for each visit.

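### For non-naïve participants the protocol gives conflicting look-back windows for flare-ups, and none reliably yields the rate from first dose to consent that the cohort comparison needs

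*Protocol*

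**What the plan says.** **Flare-ups, non-naïve participants.** Three windows appear.

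- Protocol 9.3.2.1 asks for the "Number of flare-ups over the past 12 months prior to the first marketed palovarotene intake and until the signed informed consent date". Section 9.2.7.1 matches it, taking movement-mobility history including flare-ups "over the past 12 months prior to the first marketed palovarotene intake and until Baseline Visit".
- Table 3 note l reads: "This includes number of flare-ups over the past 12 months before the first marketed palovarotene intake". It does not mention the time from first intake to consent.
- Section 9.3.2.8 makes no distinction by cohort: "At Baseline, the investigator will ask the participant how many flare-ups they experienced over the past 12 months". Section 9.7.3.4 reports on that footing: "The number of flare-ups over the past 12 months prior to baseline and since the last visit will be presented for each visit".

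For the other participants, 9.3.2.1 sets a fixed window: "12 months preceding the signed informed consent date for exposed naïve or unexposed participants".

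**Movement-mobility history, non-naïve participants.** Section 9.3.2.1 takes it "over the past 12 months prior to the first marketed palovarotene intake and until the signed informed consent date for exposed non-naïve patients", whereas 9.3.2.8 limits it to the 12 months before the Baseline Visit. Each mobility event has a start date. Flare-ups are described only as a number.

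**Analysis.** Section 9.7.3.4 lists annualised flare-up frequency first among the outcomes compared between cohorts. It sets Day 1 at the first marketed dose for naïve and non-naïve exposed participants alike, and at consent for unexposed participants. For mobility, 9.7.3.3 states: "Actual values as well as the change from the Baseline Visit in number of impacted locations per patient will be presented annually".

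**The concern.** Under 9.3.2.1 the non-naïve history is 12 months plus the time from first marketed dose to consent. That lag has no cap, differs between participants and is treated time, so untreated and treated flare-ups fall into one number. The comparison in 9.7.3.4 counts the same lag as exposed follow-up, so it needs the flare-ups that occurred within it and only those.

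Two things are at stake. First, the pre-consent treated experience of the non-naïve group could be lost to one of the key between-cohort comparisons, or filled in differently by sites following different sections. Second, if a history of variable length were used whole as the baseline for the yearly number of impacted locations, later years would look better merely because they are shorter.

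**Working it through.** The plan states no figure on this point, so there is none to reproduce. Let T be the months from first marketed intake to consent, treating consent and Baseline Visit as the same date. T is known for each participant because treatment start dates are collected (9.3.2.9), but the protocol gives no typical value. The lags and rates below are assumptions.

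**1. What each flare-up window yields for the interval from first intake to consent**

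| Source | Window | Flare-ups in the T treated months |
|---|---|---|
| 9.3.2.1, 9.2.7.1 | 12 months before intake, plus T | Included, but pooled with 12 untreated months |
| Table 3 note l | 12 months before intake | Not collected |
| 9.3.2.8, 9.7.3.4 | 12 months before Baseline | T above 12: the first T − 12 treated months are lost. T below 12: mixed with 12 − T untreated months |

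Only the last window, with T of exactly 12 months, gives the required count.

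**2. Size of the ambiguity in the pooled count.** Take T = 24 and 4 flare-ups. If k of the 4 fell after first intake, the on-drug rate is k/2 per year, and k can be 0, 1, 2, 3 or 4:

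- possible on-drug rates: 0, 0.5, 1.0, 1.5 or 2.0 per year.

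A crude rate over the whole window can be formed, but it answers another question. With a true rate of 2 per year before intake and 1 per year on drug:

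- count = 2 × 1 + 1 × 2 = 4;
- crude rate = 4/3 = 1.33 per year, against a true on-drug rate of 1.0.

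**3. Size of the ambiguity with the 12-month window.** With T = 6 and 2 reported flare-ups, the treated half-year may hold 0 to 2 of them, so the on-drug rate lies between 0 and 2/0.5 = 4 per year. With T = 24, half of the treated time before consent has no count.

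**4. Mobility, only if the history were used uncut.** With a constant event rate and no drug effect, the baseline count is (12 + T)/12 times the annual count. The apparent fall is therefore T/(12 + T):

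- T = 6: 6/18 = 33%
- T = 12: 12/24 = 50%
- T = 24: 24/36 = 67%

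Section 9.7.3.3 counts impacted locations, which can repeat. Assume 15 locations at equal hazard and λ events per year. The expected number of distinct locations in y years is 15(1 − exp(−λy/15)). For λ = 2 and T = 24, the baseline value is 15(1 − exp(−6/15)) = 4.95 and the annual value is 15(1 − exp(−2/15)) = 1.87, a fall of 62%. Over λ = 1 to 3 the fall is 30–32% at T = 6, 45–48% at T = 12 and 60–64% at T = 24.

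If the baseline is cut to 12 months, the spurious change under a constant rate is 0 in both versions.

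**The case against.** A reader might infer that the annualised flare-up rate cannot be formed at all. The protocol does not support that. Follow-up visits record flare-ups since the last visit, so the rate after consent can be formed in every cohort. Naïve and unexposed participants have a fixed 12-month history and are unaffected. What is lost is the non-naïve rate from first dose to consent.

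A reader might also infer that the study will show a false improvement. For flare-ups, no change from baseline is planned. For mobility, the start dates allow a 12-month window to be cut, the analysis is stated to be annual, and no section says that the uncut history is the comparator. The percentages in step 4 describe a mistake that the protocol permits but does not prescribe. The same holds for charging untreated flare-ups to palovarotene: no section divides the pooled count by time since first dose.

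Note l might be reconciled with 9.3.2.1, since it says what the history includes and the Table 3 column starts at first intake. That reading returns to the pooled count, still unsplit and still at odds with 9.3.2.8 and 9.7.3.4.

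Other data items do not clearly fill the gap:

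- Table 3 has no retrospective entry for mobility changes including flare-ups.
- Flare-ups are ordinarily not adverse events (11.1.1).
- Dated mobility events miss flare-ups without mobility impact, and section 7.1 notes that some flare-ups regress spontaneously.
- Flare-up treatment dates capture only treated episodes.
- The time since last flare-up in the propensity model would date one episode, not split a count.

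It stands that the primary endpoints are untouched, the analyses are descriptive, and only one subgroup's retrospective history is affected.

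**Conclusion.** The concern holds as a contradiction between sections with a specific loss of data. None of the stated windows reliably gives the non-naïve flare-up count between first marketed intake and consent, which the 9.7.3.4 comparison counts as exposed time. This conclusion needs no assumed rate. It rests on the wording of the windows, the index date, and flare-ups being described as a number without dates.

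The mobility part is conditional: bias towards improvement arises only if the variable-length history is used whole. All sizes shown are illustrative, because the protocol gives no lag, event rate or share of non-naïve participants, and the effect on the final comparison cannot be predicted.

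The point ranks below those that must be resolved before the study can proceed. It should still be corrected early. Data collection was planned from Q4 2024, the counts rely on participants' recall, and a pooled undated number cannot be separated at analysis.

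**What to change.** - **One set of windows.** State the same non-naïve windows in Table 3 note l and sections 9.2.7.1, 9.3.2.1, 9.3.2.8 and 9.7.3.4.
- **Two flare-up counts.** For non-naïve participants record (A) the 12 months before first marketed intake and (B) first marketed intake to consent. Recording onset dates would serve equally. Section 9.3.2.7 already gives fractures between first intake and consent a form of their own.
- **Mobility history.** Split it at first marketed intake using the start dates already collected. In 9.7.3.3 name a 12-month window as the baseline for the yearly change in impacted locations.
- **Person-time.** Divide each count by its own observation time, and treat B as on-treatment time in the index-date comparison.

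The cost is one extra eCRF count for non-naïve participants, aligned wording in the protocol and SAP, and a site query for any non-naïve participant already enrolled under the pooled item. No visit or assessment is added.
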